7. ANALYSIS SETS

7.1 SCREENED SET

The screened set will include all patients who provide written informed consent. This set will be used only for the purpose of describing patient disposition.

7.2 SAFETY SET

The safety set will include all patients who receive at least 1 dose of investigational medicinal product (IMP). This analysis set will be used for all safety analyses.

7.3 INTENT-TO-TREAT SET

The intent-to-treat (ITT) set will include all patients enrolled. This analysis set will be used for efficacy endpoints. ITT should be identical to the Safety set, i.e. all enrolled patients who received at least one dose of IMP. Enrolled patients are defined as Informed Consent Form (ICF) signed and all eligibility criteria are met.

7.4 PHARMACOKINETIC SET

The PK set will include all patients in the ITT set who receive IMP and have at least 1 evaluable post-dose concentration measurement.

7.5 PHARMACODYNAMIC SET

The PD set will include all patients in the ITT set who receive IMP and have at least 1 evaluable post-dose PD measurement.

8. ANALYTICAL PLAN AND STATISTICAL METHODS

8.1 GENERAL CONVENTIONS AND STATISTICAL CONSIDERATIONS

All statistical analyses will be performed, and outputs (TFLs) will be created using the SAS system version 9.4 or higher.

Data collected in this study will be presented in patient data listings and summary tables.

Descriptive statistics (number of patients with non-missing values, arithmetic mean, standard deviation (SD), median, first quartile [Q1], third quartile [Q3], minimum, and maximum) will be presented for continuous variables. For all PK parameters, the coefficient of variation (CV), geometric mean, and corresponding 95% confidence interval (CI) and geometric CV will be added to the summaries. All raw data will be presented to the original number of decimal places. Means and medians will be presented to 1 more decimal place than in the raw data. Standard deviations will be presented to 2 more decimal places than in the raw data.

• Geometric mean is calculated as follows:

$$\mu_g = \exp\left(\frac{\sum_{i=1}^n \ln x_i}{n}\right)$$

Where x_i is the value of interest for each patient.

• CV is calculated using SD and mean using the following formula:

$$CV (\%) = \frac{SD}{Mean} x 100$$

Geometric CV is calculated as follows:

$$GCV (\%) = \sqrt{\exp(SD^2) - 1} x 100$$

Where SD is the standard deviation of the log-transformed value of interest for each patient.

Frequency distributions (counts and percentages) will be presented for categorical variables. Percentages will be suppressed when the count is zero, however the category will still be displayed. If not specified otherwise, the number of observations with non-missing values will be the denominator for percentage calculation. Percentages will be presented to 1 decimal place. Further details on the handling of missing observations are given in Section §8.4.

Safety laboratory results reported as below or above limits of quantification, e.g., "<x.x", "<=x.x", ">x.x" or ">=x.x", will be summarized in the tables using the reported limit of quantification (LOQ). The listings will show the result as reported.

Calculations using dates (e.g., relative day after the first dose of the study drug) will adhere to the following conventions:

- Study days on or after the start day of study treatment will be calculated as the difference between the date of interest (TARGET DATE) and the first date of dosing of study treatment (TSTART) plus 1 day. The generalized calculation algorithm for the relative day is the following:
 - o If TARGET DATE ≥ TSTART then STUDY DAY = (TARGET DATE TSTART) + 1.
 - Else use STUDY DAY = TARGET DATE TSTART.

Note that Study Day 1 is the first day of study treatment. Study days on or before Day 1 are reflective of observations obtained during the baseline/Screening period.

Intervals that are presented in weeks will be transformed from days to weeks by using (with rounding

Page 18 of 39

to 4 decimal places) the following conversion formula:

• Intervals that are presented in months will be transformed from days to months by using (with rounding to 4 decimal places) the following conversion formula:

• Intervals that are presented in years will be transformed from days to years by using (with rounding to 4 decimal places) the following conversion formula:

All data collected will be presented in the data listings.

All the analyses will be descriptive, no hypothesis testing will be performed.

8.2 DEFINITION OF BASELINE, AND CHANGE FROM BASELINE

Baseline will be defined as the value at Baseline visit (i.e., visit 2). For TA-TMA related variables, the value reported on the baseline TA-TMA form will be considered as baseline. If no assessment is available at the Baseline visit, then the last assessment during the screening period will be used. As a general rule, the last assessment prior to the first dose of the study treatment will be considered as baseline. On study day 1, if assessment time is available and before the first infusion, then it will be considered as baseline. Assessments of height and weight and questionnaires completed at study day 1 will be considered as baseline if no time stamp of the assessment is available. If assessment time is available and after the infusion, then it will be presented as study day 1 of the treatment period and not as baseline.

Change from Baseline will be calculated using the following formula:

Change from Baseline = Post baseline value - Baseline value

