# Baseline, efficacy, safety, pharmacokinetic, pharmacodynamic and pharmacogenetics assessments

# 6.5.1 Medical history

Medical history will be recorded at screening. Investigators should document the occurrence, signs, and symptoms of the patient's preexisting conditions, including all prior significant illnesses, up to and including 1 year before enrollment in the study. Additional preexisting conditions that started before and are ongoing at the date of enrollment are to be regarded as current medical conditions. Medical history will include alcohol consumption and smoking history, if applicable.

Information about HSCT and related complications will be also collected, including underlying disease diagnosis; donor type; HLA mismatch; stem cell source; type and start date of conditioning regimen; conditioning medications; date of transplant; transplant manipulation; donor chimerism; date of confirmed engraftment; GVHD date of onset; GVHD grade according to the International Bone Marrow Transplant Registry severity Index [22]; presence of infections; presence of donor specific antibodies; posttransplant treatments and date (e.g., donor lymphocyte infusion, stem cell boost, growth factors; infusion of antiviral T cells); GVHD prophylaxis.

Information about TA-TMA will be collected including date of diagnosis (defined as the earliest date when all required laboratory criteria outlined in Inclusion Criterion #3 are met); diagnostic laboratory markers; initial management; and presence of signs and symptoms of end organ injury.

Baseline end organ injury will be evaluated as follows, with associated medications:

Confidential Page 46 of 89

- a. Kidney: doubling of serum creatinine compared with pre-HSCT level or patient receiving renal replacement therapy or proteinuria ≥ 30 mg/dL OR rUPCR ≥ 1 mg/mg.
- b. Lungs: hypoxemia or any need for noninvasive or invasive positive pressure ventilation.
- c. Cardiovascular: pulmonary hypertension diagnosed by a cardiologist using cardiac catheterization, or pulmonary hypertension criteria on echocardiography or arterial hypertension, defined by systolic BP  $\geq$  140 mmHg and/or diastolic BP  $\geq$  90 mmHg at baseline or hypertension requiring > 2 medications (excluding diuretics).
- d. Serositis: clinically significant pleural effusion or pericardial effusion requiring surgical therapy (e.g., pericardiocentesis/ thoracocentesis).
- e. CNS: seizures attributable to posterior reversible encephalopathy syndrome.

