#### 8.3.1 General statistical issues

All endpoints will be evaluated with descriptive statistics. PK and PD may also be presented graphically.

Baseline will be defined as the Baseline visit. If no assessment is available at the Baseline visit, then the last assessment during the screening period will be used. If multiple values assessments are available, then the last assessment prior to first dose will be used.

No statistical tests will be performed.

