8.3 STUDY VISITS AND ANALYSIS WINDOWS

Data will be summarized and analyzed based on the list of visits specified in Table 1 – Study Visits and Analysis Windows.

Table 1 – Study Visits and Analysis Windows

Period	Visit	Target Study Day	Analysis Window (study day)	Interval (days)
Screening	Screening	-14	-14 to -1	NA
	Baseline	Last assessment prior to first dose of the study treatment. On study day 1, If assessment time is available and before the first infusion or if assessment of height and weight, and questionnaires then it will be considered as baseline.		
Treatment	Day 1	1	1	1

Page 19 of 39

	Week 1	8	2-11	10
	Week 2	15	12-18	7
	Week 3	22	19-25	7
	Week 4	29	26-35	10
	Week 6	43	36-50	14
	Week 8	57	51-64	14
	Week 10	71	65-78	14
	Week 12	85	79-92	14
	Week 12**	85	79-99	21
Optional Treatment	Week 14	99	93-106	14
	Week 16	113	107-127	21
Follow-up	Week 16**	113	100-127	28
	Week 20	141	128-155	28
	Week 24	169	156-183	28

^{*} Study day 1 is the day of the first dose of pegcetacoplan.

Planned visits, as recorded in the eCRF, will be considered first. Only if there is no planned visit recorded in the eCRF (or a planned visit which contains missing data) unscheduled visits will be considered.

If more than 1 record is within the same analysis visit window, the record closest to the target day with non-missing data (the day of the planned visit according to protocol schedule of assessments) will be used in the analysis.

If no planned or unscheduled visit is within the analysis window the data for the visit will remain as missing.

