8.7.2 MEDICAL HISTORY AND CURRENT MEDICAL CONDITIONS

Medical history (conditions that ended before the date of enrollment) and current medical conditions (those that started before and were ongoing at the date of enrollment) will be coded using the Medical Dictionary for Regulatory Activities (MedDRA) version current at the time of DBL and tabulated by System Organ Class (SOC) and Preferred Term (PT).

Baseline TA-TMA data will be summarized using the following variables:

- The platelet value at the diagnosis (10^9/L),
- The highest platelet value achieved after transplant (10^9/L),
- The LDH value at diagnosis (U/L),
- Diagnosis of TA-TMA established as per laboratory/clinical markers indicating TMA.
 - o Presence of schistocytes in the peripheral blood smear (yes or no),
 - Absolute number of schistocytes per high power field in the peripheral blood smear (per hpf),
 - o Was any biopsy performed to confirm the histologic diagnosis of TA-TMA (yes or no),
 - If yes, sample location,
 - o De novo anemia at diagnosis (yes or no)
 - The most recent pre-transfusion hemoglobin (Hb) level at diagnosis (g/dL),
 - Proteinuria at diagnosis (yes or no),

Page 21 of 39

- The most recent rUPCR value at diagnosis (mg/mg).
- The most recent proteinuria value at diagnosis (mg/dL),
- Elevated plasma concentration of Sc5b-9 above ULN (yes or no),
 - Sc5b-9 level at diagnosis (ng/mL),
- Arterial hypertension defined by systolic blood pressure (BP) ≥ 140 mmHg and/or diastolic BP ≥ 90 mmHg (yes or no),
 - The pre-antihypertensive therapy systolic blood pressure (mmHg),
 - The pre-antihypertensive therapy diastolic blood pressure (mmHg),
 - Patients taking any antihypertension medication (yes or no),
 - Number of ongoing medications, excluding diuretics,
 - 0 medication,
 - ≤ 2 medications,
 - > 2 medications,
- o Time between HSCT and TA-TMA diagnosis (days),
- o Time between TA-TMA diagnosis and study enrollment (days).
- o TA-TMA persisting despite initial management of any triggering condition (yes or no),
- o Any sign/symptom of kidney dysfunction (yes or no),
 - The most recent serum creatinine value (mg/dL),
 - The last serum creatinine value pre-transplant (mg/dL),
 - Patients requiring renal replacement therapy (yes or no),
- Any sign/symptom of lungs dysfunction (yes or no),
 - The lowest oxygen level in the blood (%),
 - Patients receiving noninvasive positive pressure ventilation (yes or no),

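### SAP 8.2 takes baseline for undefined TA-TMA related variables from a form; if this covers rUPCR, the 50% reduction may run from diagnosis, not from the last pre-dose value

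*SAP*

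**What the plan says.** SAP 8.2 starts from the Visit 2 value and then makes an exception: "For TA-TMA related variables, the value reported on the baseline TA-TMA form will be considered as baseline". Later in the same paragraph it states: "As a general rule, the last assessment prior to the first dose of the study treatment will be considered as baseline". The paragraph neither lists the variables covered by the exception nor says which rule takes precedence.

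SAP Table 1 (section 8.3) describes the baseline row as "Last assessment prior to first dose of the study treatment", with no form exception. Protocol 8.3.1 says "Baseline will be defined as the Baseline visit", falls back to the last screening assessment, and takes the last pre-dose value if there are several.

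SAP 8.7.2 lists the baseline TA-TMA data to be summarised. The rUPCR item reads "The most recent rUPCR value at diagnosis (mg/mg"). The same list includes "Time between TA-TMA diagnosis and study enrollment (days"), so the SAP expects the two dates to differ. The creatinine item is labelled differently: "The most recent serum creatinine value (mg/dL").

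SAP Appendix I (13.1) includes the Baseline TA-TMA form among its sources for clinical response. It tests for a fall of at least 50% from a quantity called rUPCR_baseline, whose source it does not name. SAP Appendix II (13.2) requires the same fall for TMA response but lists only the transfusion and central laboratory forms.

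**The concern.** A percentage reduction depends on its starting value. Protocol 6.5.1 dates the diagnosis at the earliest point when the laboratory criteria of Inclusion Criterion 3 are met. Criterion 4 then requires the disease to persist despite initial management of any trigger. rUPCR can therefore move between diagnosis and first dose for reasons unrelated to pegcetacoplan. Measured from diagnosis, that movement enters the response: a pre-dose fall is credited to treatment, and a pre-dose rise hides part of a treatment effect.

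The renal component matters because entry requires rUPCR of at least 1 mg/mg (criterion 5), and Protocol 6.5.1 counts "proteinuria ≥ 30 mg/dL OR rUPCR ≥ 1 mg/mg" as baseline kidney injury. If patients are coded that way, the renal route to clinical response is open to all 12, and the rUPCR fall alone satisfies it. For TMA response the same fall is mandatory. These derivations also feed the Week 12 responses and the time to and duration of response; clinical response also sets the denominator for relapse. With a single arm there is no comparator to reveal a baseline effect.

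**Working it through.** **1. The texts side by side.**

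| Place | Baseline for rUPCR |
|---|---|
| Protocol 8.3.1 | Baseline visit, otherwise last screening; last pre-dose value if several |
| SAP Table 1 | Last pre-dose value |
| SAP 8.2, general rule | Last pre-dose value |
| SAP 8.2, form sentence | Value on the baseline TA-TMA form, if rUPCR is covered |
| Appendix I (clinical response) | Source not named; central laboratory and Baseline TA-TMA forms both listed |
| Appendix II (TMA response) | Source not named; Baseline TA-TMA form not listed |

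SAP section 10 declares two departures: the target medical event analysis and the dropped interim analysis. Neither concerns baseline. The SAP revision history records that the baseline derivation was updated, but does not say which variables the form sentence covers.

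**2. The plan's own figure.** The only response-rate figure is the 72% probability of at least 8 responders among 12 at a true rate of 70% (Protocol 8.1, SAP 5). The exact binomial tail is 0.7237, so it reproduces. It does not depend on the baseline rule.

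**3. Where the two baselines disagree.** Let D be rUPCR at diagnosis, P the last pre-dose value, W the value at the response visit, and c = P/D − 1 the relative pre-dose change. The documents give no value for c; all values below are assumed.

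- From the pre-dose value the criterion is W ≤ 0.5 P, an on-treatment fall of 50%.
- From diagnosis it is W ≤ 0.5 D = 0.5 P/(1 + c), an on-treatment fall of 1 − 0.5/(1 + c).

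| Assumed c | On-treatment fall needed if measured from diagnosis |
|---|---|
| −50% | 1 − 0.5/0.5 = 0% |
| −30% | 1 − 0.5/0.7 = 28.6% |
| −20% | 1 − 0.5/0.8 = 37.5% |
| 0 | 50% |
| +25% | 1 − 0.5/1.25 = 60% |
| +50% | 1 − 0.5/1.5 = 66.7% |
| +100% | 1 − 0.5/2 = 75% |

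The window of disagreement lies between the tabulated figure and 50%. For c = −30%, falls of 28.6% to under 50% count only from diagnosis. For c = +25%, falls of 50% to under 60% count only from the pre-dose value.

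**4. Two assumed patients (mg/mg).**

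- Diagnosis 2.0, Day 1 1.4, Week 24 1.0. From diagnosis: 1 − 1.0/2.0 = 50.0%, met. From Day 1: 1 − 1.0/1.4 = 28.6%, not met.
- Diagnosis 1.2, Day 1 1.5, Week 24 0.7. From diagnosis: 1 − 0.7/1.2 = 41.7%, not met. From Day 1: 1 − 0.7/1.5 = 53.3%, met.

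If Appendix I used the form value and Appendix II the central laboratory value, each patient would meet the rUPCR criterion for one endpoint and fail it for the other at the same visit.

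**5. Weight of one patient.** 1/12 = 8.3 points. Clopper-Pearson 95% intervals, the method in SAP 8.8.2.2: 7/12 = 58.3% (27.7 to 84.8); 8/12 = 66.7% (34.9 to 90.1); 9/12 = 75.0% (42.8 to 94.5).

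**The case against.** The strongest defence is that the documents, read together, favour the ordinary baseline. rUPCR is a scheduled test at screening, baseline and every later visit (Protocol Table 1). The general rule in SAP 8.2 follows the form sentence, and SAP Table 1 has no exception. The programming note in Appendix I puts central laboratory values first. Appendix I needs the Baseline TA-TMA form for its organ items in any case, so listing it proves nothing about rUPCR. SAP 8.7.2 is a patient-characteristics section: it does not say that its list reproduces the form or feeds the response derivation, and its items mix time points. All this stands, and it is why the point is conditional. It does not remove the problem. SAP 8.2 states the form rule without limits, and a programmer applying it literally could take the at-diagnosis rUPCR.

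It is also fair that reclassification needs several things at once: a material pre-dose change, an on-treatment fall inside the window, and LDH and platelet criteria met. For clinical response, no other renal or organ criterion may be met either. The intervals above overlap almost completely, and no hypothesis is tested.

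A reader might infer that the baseline could be a post-dose value. The documents do not support that. Diagnosis is required for entry, so an at-diagnosis value precedes first dose. The question is only whether it is the last pre-dose value. Nor does a missing baseline value leave a gap: SAP 8.2 and Protocol 8.3.1 both fall back to the last screening assessment.

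**Conclusion.** The point holds as a conflict between baseline rules with a conditional consequence. What is certain is that the form rule in SAP 8.2 has no defined scope, disagrees with the protocol and with the SAP's own general rule, and is not declared in section 10. What is conditional is that it reaches rUPCR. If it does, clinical response may be measured from diagnosis while TMA response is measured from the last pre-dose value.

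A reader might go further and infer an inflated response rate. That is not supported: the pre-dose change is unknown and can go either way. The disagreement windows rest wholly on assumed changes, and the 8.3 points are the weight of one reclassified patient, not an estimate of bias. Severity is minor to moderate because the endpoints are secondary and descriptive.

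**What to change.** Before database lock:

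1. State in SAP 8.2 that baseline for rUPCR and every other change-based response variable is the last value before first dose (Visit 2, otherwise last screening), as in Protocol 8.3.1.
2. Restrict the form rule to a named list of variables.
3. Refer to that same rUPCR baseline in Appendices I and II.
4. Keep at-diagnosis values as descriptors only.
5. If any departure from Protocol 8.3.1 is retained, list it in SAP section 10.

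The cost is SAP wording and one baseline flag. No new data are needed: Protocol Table 1 schedules rUPCR at screening and Day 1, and its footnote p lets the Day 1 collection be omitted only when screening samples were taken on Day -1, so the schedule already provides a late pre-dose value. The reported response rate may change in either direction, which is a reason to settle the rule before results are seen.

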8.3 STUDY VISITS AND ANALYSIS WINDOWS

Data will be summarized and analyzed based on the list of visits specified in Table 1 – Study Visits and Analysis Windows.

Table 1 – Study Visits and Analysis Windows

Period	Visit	Target Study Day	Analysis Window (study day)	Interval (days)
Screening	Screening	-14	-14 to -1	NA
	Baseline	Last assessment prior to first dose of the study treatment. On study day 1, If assessment time is available and before the first infusion or if assessment of height and weight, and questionnaires then it will be considered as baseline.		
Treatment	Day 1	1	1	1

Page 19 of 39

	Week 1	8	2-11	10
	Week 2	15	12-18	7
	Week 3	22	19-25	7
	Week 4	29	26-35	10
	Week 6	43	36-50	14
	Week 8	57	51-64	14
	Week 10	71	65-78	14
	Week 12	85	79-92	14
	Week 12**	85	79-99	21
Optional Treatment	Week 14	99	93-106	14
	Week 16	113	107-127	21
Follow-up	Week 16**	113	100-127	28
	Week 20	141	128-155	28
	Week 24	169	156-183	28

^{*} Study day 1 is the day of the first dose of pegcetacoplan.

Planned visits, as recorded in the eCRF, will be considered first. Only if there is no planned visit recorded in the eCRF (or a planned visit which contains missing data) unscheduled visits will be considered.

If more than 1 record is within the same analysis visit window, the record closest to the target day with non-missing data (the day of the planned visit according to protocol schedule of assessments) will be used in the analysis.

If no planned or unscheduled visit is within the analysis window the data for the visit will remain as missing.

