#### 6.5.5.3 Vital signs

Vital signs (body temperature, respiration rate, heart rate and systolic and diastolic BP measurements) will be evaluated per institutional practices at the visits indicated in the schedule of assessments (Table 1).

When the IMP is administered at the study site, vital signs will be measured within 2 hours before dosing and venipuncture (and ECG, if applicable), and at 30 minutes (± 5 minutes) postdose.

Vital signs measurements will be repeated if clinically significant or if machine/equipment errors occur. Out-of-range BP, respiratory rate, or heart rate measurements will be repeated at the investigator's discretion. Any confirmed, clinically significant vital signs measurements must be reported as AEs (see Section 6.5.5.1.1 for details).

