- f On dosing Days 1, 3 and 5, PK samples will be taken up to 30 minutes predose and at 15 minutes (± 5 min), 30 minutes (± 5 min), 1 hour (± 10 min), 4 hours (± 10 min), 8 hours (± 30 min), and 24 hours (± 30 min) postdose. From Day 8 and onwards, PK samples will be taken predose at all other visits.

Confidential

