8.7.5 STUDY TREATMENT COMPLIANCE

All the details related to the IMP administration originate from the "Pegcetacoplan administration" eCRF form, regardless of the infusion site. The clinic and non-clinic administrations will be included in the calculation of compliance.

Two measures of compliance will be calculated in the study: infusion-level compliance and volume-level compliance.

Infusion-level compliance is defined as the total number of study infusions administered from the first infusion to the last infusion, multiplied by 100 and divided by the expected number of infusions. In case of premature treatment discontinuation, the expected number of infusions will be calculated for the period up to treatment discontinuation. The exact number of expected infusions will be calculated based on the total number of days from the date of the first study drug infusion till the date of treatment discontinuation. The rules are as follows:

- If time on treatment is less than 7 days, then expected number of infusions = floor ((time on treatment (days)+1)/2)
- If time on treatment is 7 days or more, then expected number of infusions = 3 + floor ((time on treatment (days) 5)/3)

Floor in the above derivations refers to rounding down to the closest integer.

Volume-level compliance will be defined as the total volume of study drug administered divided by the total volume that had to be administered (based on the total amount of infusions expected, calculated as described above).

Both compliance measures will be summarized as numeric values. In addition, the number and percentage of subjects who had treatment compliance in the three categories [80%; 90%], [90%; 100%] and [80%, 100%] will be presented.

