Actual sampling time from start of infusion will be used for parameter estimation except for predose data points, which will be set to 0. If actual sampling time is missing, the planned time should be used. If a predose sample is taken after dosing, it will be taken as missing. AUC is calculated using the linear-log trapezoidal rule.

The following PK parameters will be calculated:

Day 1 (induction phase):

- AUC_{0-tau}: area under the concentration-time curve over the dosing interval, as calculated by the linear-log trapezoidal method.
- C_{max}: maximum observed serum concentration.
- T_{max}: time to the maximum observed serum concentration. If the maximum value occurs at more than 1 time point, T_{max} is defined as the first time point with this value.

Day 3 (induction phase):

- AUC_{0-tau}:
- C_{max}
- T_{max}: If the maximum value occurs at more than 1 time point, T_{max} is defined as the first time point with this value.

Day 5 (induction phase):

- AUC_{0-tau}:
- C_{max}
- T_{max}: If the maximum value occurs at more than 1 time point, T_{max} is defined as the first time point with this value.

Day 8 and onwards (s.c. maintenance phase):

C_{trough}: observed serum concentration predose.

Serum PK parameters C_{max}, AUC_{tau} and T_{max} and C_{trough} concentrations will be summarized including N,

Page 25 of 39

arithmetic mean, standard deviation, coefficient of variation, minimum, maximum, Q1, Q3, and median. In addition, geometric means and corresponding 95% confidence intervals will be calculated for AUC parameters, and C_{max} . For t_{max} , the geometric mean and its 95% CI, SD are not calculated. Figures: individual pegcetacoplan concentration-time curves and mean (SD) concentration-time profiles will be created to present the repeated-dose profile obtained from Day 1 to Day 8.

Additional PK analyses may be performed if deemed appropriate.

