8.9.4 VITAL SIGNS, PHYSICAL EXAMINATION AND ECG

Summary statistics of vital signs (systolic and diastolic blood pressure, heart rate, respiration rate, and body temperature) and their changes from baseline will be presented by visit and timepoint.

Physical examination data will be presented in a listing.

The incidence of clinically significant abnormal ECG findings will be summarized by visit and timepoint.

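### The SAP's Week 1 window leaves vital signs around the Day 3 and Day 5 induction doses out of the by-visit safety summary, or may label a Day 5 reading as Week 1

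*SAP*

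**What the plan says.** **Visits and windows.** SAP 8.3 sets the frame for by-visit output: "Data will be summarized and analyzed based on the list of visits specified in Table 1". In that table the Day 1 row covers Day 1 only. The next row is Week 1, with target Day 8 and window Days 2 to 11. There is no Day 3 or Day 5 row.

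**Choice of record.** "Planned visits, as recorded in the eCRF, will be considered first"; unscheduled records are used only when the planned one is absent or has missing data. Then: "If more than 1 record is within the same analysis visit window, the record closest to the target day with non-missing data" is the one analysed. No tie-break is given.

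**Induction days.** Protocol 6.5.4 and footnote f to protocol Table 1 (repeated in Appendix 6) set serial sampling: "On dosing Days 1, 3 and 5, PK samples will be taken up to 30 minutes predose", with further samples up to 24 hours postdose. SAP 8.8.1 assigns Days 1, 3 and 5 to the induction phase and Day 8 onwards to s.c. maintenance.

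**Vital signs.** Protocol 6.5.5.3: "When the IMP is administered at the study site, vital signs will be measured within 2 hours before dosing and venipuncture", and again 30 minutes after the dose. SAP 6.1 lists change from baseline in vital signs among the primary safety endpoints. SAP 8.9.4 says of the summary statistics that "their changes from baseline will be presented by visit and timepoint".

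**The concern.** The vital-sign table is built by visit, and two of the three induction days are not visits in SAP Table 1. Their readings fall inside the Week 1 window, where they compete with the planned Day 8 visit and lose. The table can then show the haemodynamic picture around the first induction dose but not around the second or third.

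Other data types are protected. SAP 8.8.1 summarises drug concentrations by day and time postdose, and SAP 8.9.2 adds shift tables of the worst post-baseline laboratory value, including unscheduled ones. The SAP states neither device for vital signs.

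The reverse error is also possible. Where the Week 1 visit has no postdose reading, a postdose value from an induction day can be presented as Week 1, which belongs to the maintenance phase.

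The endpoint is primary, protocol 4.3 describes hypersensitivity as strongly linked to systemic pegcetacoplan, and protocol 6.2 presents the study as the drug's initial exploration in TA-TMA. A by-visit table that is silent on two induction doses, or mixes the phases, describes that endpoint incompletely.

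**Working it through.** **Inputs**
- Week 1: target Day 8, window Days 2 to 11, stated interval 10 days (SAP Table 1).
- Week 1 visit window: Day 8 ± 1, so Days 7 to 9 (protocol Table 1).
- Induction doses: Days 1, 3 and 5 (protocol 6.5.4; SAP 8.8.1).
- Planned sample: 12 patients (protocol 8.1; SAP 5).

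**Step 1: reproduce the stated window length.** 11 − 2 + 1 = 10 days, as stated. Days 3 and 5 both lie inside it.

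**Step 2: check the induction days against the compliance rule in SAP 8.7.5.** Below 7 days, expected infusions = floor((t + 1)/2). Taking t as the study day:
- t = 1: floor(2/2) = 1
- t = 3: floor(4/2) = 2
- t = 5: floor(6/2) = 3

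From 7 days, expected infusions = 3 + floor((t − 5)/3), which reaches 4 at t = 8 and 5 at t = 11. So doses fall on Days 1, 3, 5, 8 and 11 under this rule.

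**Step 3: distance to target.**
- Day 3: |3 − 8| = 5
- Day 5: |5 − 8| = 3
- Day 7, 8 or 9: 1, 0 or 1

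**Step 4: apply the closest-record rule.**

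| Days with a non-missing record | Record used as Week 1 |
|---|---|
| 3, 5, 8 | 8 |
| 3, 5, 7 | 7 |
| 3, 5, 9 | 9 |
| 3, 5, 8, 11 | 8 |
| 3, 5 | 5 |
| 3, 5, 11 | tie between 5 and 11 |

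The induction readings lose whenever the Week 1 visit has data. It makes no difference whether the eCRF holds them as planned or unscheduled: a planned record is farther from Day 8, and an unscheduled one is not considered.

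**Step 5: the postdose timepoint.** The last two rows of the table can arise here. A Week 1 visit on Day 7 or 9 does not coincide with the Day 8 dose and so has no 30-minute postdose reading. If selection is made separately for each timepoint, which the SAP does not settle, the Day 5 postdose value becomes Week 1. If the Day 11 dose was also given on site, Days 5 and 11 tie at 3 days.

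**Step 6: size.** Induction pre/postdose pairs: 12 × 3 = 36. Pairs on Days 3 and 5: 12 × 2 = 24. Share: 24/36 = 67%. Per patient, the by-visit table is assured of 1 of 3 induction doses.

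**The case against.** **The requirement is partly inferred.** Protocol 6.5.5.3 ties vital signs to the visits in protocol Table 1, which has no Day 3 or Day 5 column. Footnote f adds those days by name for PK; footnote e does not do so for vital signs. On-site induction dosing is also an inference, because part of the dosing text is blacked out. This stands as a limit, but the inference is strong: samples at 15 and 30 minutes and at 1, 4, 8 and 24 hours are hard to reconcile with dosing elsewhere, and protocol 6.4.5 describes self-administration only for s.c. doses.

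**The display may already be right.** Protocol 8.3.3.2 promises vital signs by visit and nominal time postdose, SAP 8.8.1 already tabulates PK on days outside Table 1, and the mock tables are a separate document that could include the rows. This is possible. But a timepoint within a visit does not create a visit, and mock tables with extra rows would depart from SAP 8.3 as written.

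**The safety consequence is limited.** SAP 8.1 lists all data, which is readable for 12 patients. Confirmed clinically significant vital signs must be reported as adverse events (protocol 6.5.5.3) and are tabulated with them. Hypersensitivity is covered by its own Target Medical Event category (SAP 8.9.1 and Appendix IV). Mean change in 12 patients would detect individual reactions poorly. All of this stands.

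**New rows in Table 1 would reach too far.** Table 1 governs every by-visit domain, and laboratory, ECG and biomarker data have no Day 3 or Day 5 assessment. This also stands, so the remedy should be confined to vital signs.

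**Conclusion.** The rule as written gives an incomplete by-visit table for a primary safety endpoint, and in some cases a mislabelled one. Day 3 and Day 5 vital signs are displaced whenever the Week 1 visit has data at the same timepoint; otherwise a Day 5 reading may appear as Week 1.

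The figure of 24 of 36 pairs is a ceiling. It assumes that all 12 patients receive all three induction doses on site, that both readings are taken each time, and that no induction reading stands in for Week 1.

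A reader might infer that only the first induction dose can ever appear, that vital signs around two thirds of induction doses are lost, or that hypersensitivity reactions would go unseen. The documents do not support this: a Day 5 value can enter as Week 1, every value is listed, and clinically significant readings and hypersensitivity have their own adverse-event summaries. PK summaries are unaffected. The point is worth correcting because the rule, not a shortage of data, causes the gap.

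**What to change.** Add a rule to SAP 8.9.4, applying to vital signs only:
- Vital signs around doses on Days 1, 3 and 5 are summarised by nominal day and timepoint (predose and 30 minutes postdose), with change from baseline, in the way SAP 8.8.1 treats PK concentrations. On Day 1 the predose reading is itself the baseline under SAP 8.2.
- Vital-sign readings from Days 2 to 6 are not eligible for the Week 1 record. Days 7 to 11 remain, which still contain the permitted visit days 7 to 9 and remove the tie between Days 5 and 11.

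The table would then provide for all 3 induction doses instead of 1. Change from the same-day predose value is an optional addition; the defined endpoint is change from baseline.

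**Cost:** a short SAP edit and 2 days × 2 timepoints = 4 more rows per vital sign, with the mock tables aligned if they lack them. A patient with no vital signs on Days 7 to 11 would show as missing at Week 1, which is the accurate description. No new assessments are needed, and Table 1 does not change for other domains.
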